6.3.3 Ibrutinib Overdose

Any dose of study drug in excess of that specified in this protocol is considered to be an overdose. Signs and symptoms of an overdose that meet any Serious Adverse Event criterion must be reported as a Serious Adverse Event in the appropriate time frame and documented as clinical sequelae to an overdose.

There is no specific experience in the management of ibrutinib overdose in subjects. No maximum tolerated dose (MTD) was reached in the Phase 1 study in which subjects received up to 12.5 mg/kg/day (1400 mg/day). Healthy subjects were exposed to up to single dose of 1,680 mg. One healthy subject experienced reversible Grade 4 hepatic enzyme increases (AST and ALT) after a dose of 1,680 mg. Subjects who ingested more than the recommended dosage should be closely monitored and given appropriate supportive treatment. Refer to Section 11.4.3.8 for further information regarding special reporting situations as a result of overdose

Ibrutinib + GA101 - Obinutuzumab. University of California, San Diego

Dose Modifications and delays for GA101 – Obinutuzumab

Splitting the first dose of GA101 – Obinutuzumab in Cycle 1 is mandatory. The first dose (1,000 mg) must be administered over Days 1 and 2 (100 mg on Day 1 and 900 mg on Day 2). Infusions should be interrupted or slowed if subjects experience infusion reactions (see Section 6.2.11). If a planned dose of GA101 - Obinutuzumab is missed, it should be administered as soon as possible and the next cycle should begin 28 days later. Do not wait until the next planned dose.

No reduction in the dose of GA101 - Obinutuzumab is allowed. A dose delay of up to 8 weeks is permitted for GA101 - Obinutuzumab to allow recovery of hematologic toxicities to \leq Grade 2 or non-hematologic toxicities to Grade 1 or baseline level. If the treatment is delayed for more than 8 weeks because there is no improvement of cytopenia to \leq Grade 2, treatment under this protocol will be discontinued and the subject will continue in follow-up until the beginning of new treatment or death.

If a subject experiences grade 3 or 4 cytopenia, the guidelines for GA101 – Obinutuzumab and Ibrutinib dose-delay are outlined in Table 7:

Table 7 Dose Modification for Cytopenias

Grade	GA101 - Obinutuzumab	Ibrutinib

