Grade 3 or 4 cytopenia ^{a, c}	Delay dose for a maximum of 8 weeks. If improvement to ≤ Grade 2 ^b , administer full dose. If delay more than 8 weeks because there is no improvement of cytopenia < Grade 3, subject will be withdrawn from the study treatment but will continue in follow-up until the beginning of new treatment or death.	Hold Ibrutinib until recovery to Grade ≤ 1 ^b ; restart Ibrutinib at 420 mg daily. For subjects with recurrent episodes of grade 3 - 4 AEs a dose modification action is described in table 4 (see section 6.3.1). Ibrutinib may be held for a maximum of 28 consecutive days of toxicity. Ibrutinib should be discontinued in the event of a toxicity lasting > 28 days and the subject will be withdrawn from the study treatment but will continue in follow-up until the beginning of new treatment, death or assessment of TFS and OS.

Ibrutinib + GA101 – Obinutuzumab. University of California, San Diego

Grade 1 or 2 cytopenia ^{a, c}	No dose reduction or delay	No dose reduction.
--	----------------------------	--------------------

- a In subjects with cytopenia at baseline, dose modifications will be based on the IWCLL Guidelines for hematological toxicity in CLL studies (Hallek et al., 2008). For subjects with a normal neutrophil count, platelet count, and/or hemoglobin value at baseline, the NCI-CTCAE v4.0 grading system will be used.
 - b Or baseline.

° Subjects with cytopenia at baseline should have hemoglobin ≥ 8 g/dL, platelets count ≥ 40 x10³/mm³ and absolute neutrophil count (ANC) ≥ 1.0×10^9 cells/L in order to proceed with the study treatment. Transfusion and Growth factors will be permitted and must be documented in the medical chart.

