Appendix 3 IWCLL Guideline for Grading Scale for Hematological Toxicity in CLL Studies

Grade*	Decrease in platelets† or Hb‡ (nadir) from pretreatment value, %	Absolute neutrophil count/μL§ (nadir)
0	No change to 10%	≥ 2000
1	11%-24%	≥ 1500 and < 2000
2	25%-49%	\geq 1000 and $<$ 1500
3	50%-74%	≥ 500 and < 1000
4	≥ 75%	< 500

*Grades: 1, mild; 2, moderate; 3, severe; 4, life-threatening; 5, fatal. Death occurring as a result of toxicity at any level of decrease from pretreatment will be recorded as grade 5.

†Platelet counts must be below normal levels for grades 1 to 4. If, at any level of decrease, the platelet count is $<20\times10^9/L$ (20 $000/\mu L$), this will be considered grade 4 toxicity, unless a severe or life-threatening decrease in the initial platelet count (eg, $20\times10^9/L$ [20 $000/\mu L$]) was present pretreatment, in which case the patient is not evaluable for toxicity referable to platelet counts.

‡Hb levels must be below normal levels for grades 1 to 4. Baseline and subsequent Hb determinations must be performed before any given transfusions. The use of erythropoietin is irrelevant for the grading of toxicity but should be documented.

§If the absolute neutrophil count (ANC) reaches $< 1 \times 10^9$ /L (1000/ μ L), it should be judged to be grade 3 toxicity. Other decreases in the white blood cell count, or in circulating neutrophils, are not to be considered because a decrease in the white blood cell count is a desired therapeutic endpoint. A gradual decrease in granulocytes is not a reliable index in CLL for stepwise grading of toxicity. If the ANC was $< 1 \times 10^9$ /L (1000/ μ L) before therapy, the patient is not evaluable for toxicity referable to the ANC. The use of growth factors such as G-CSF is not relevant to the grading of toxicity, but should be documented.

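### Table 7 ends study treatment for the same cytopenia at two different limits (8 weeks and 28 days), and does not say whether note c's count floors override the no-delay rule for Grade 1–2

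*Combined protocol and SAP*

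**What the plan says.** Table 7 stands in the part on obinutuzumab dose modifications and delays. The contents list and Section 10.2.5 number it 6.3.4; in the body the heading has no number and follows Section 6.3.3.

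**Grade 3–4 row, obinutuzumab cell.** "Delay dose for a maximum of 8 weeks", with the full dose on improvement to Grade 2 or better, or to baseline (note b). If the delay exceeds 8 weeks without improvement, the subject comes off study treatment and stays in follow-up. The text before the table repeats this: "A dose delay of up to 8 weeks is permitted for GA101 - Obinutuzumab to allow recovery of hematologic toxicities to" Grade 2 or better, after which all protocol treatment stops.

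**Grade 3–4 row, ibrutinib cell.** Hold until Grade 1 or better, or baseline, for at most 28 consecutive days. Ibrutinib is to be discontinued for a "toxicity lasting > 28 days and the subject will be withdrawn from the study treatment".

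**Section 6.3.1.** Same 28-day limit, for toxicity above Grade 1, but the stated consequence is discontinuation of ibrutinib only.

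**Grade 1–2 row.** The obinutuzumab cell says "No dose reduction or delay". The ibrutinib cell excludes dose reduction and does not mention delay.

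**Notes.** Note a: "In subjects with cytopenia at baseline, dose modifications will be based on the IWCLL Guidelines for hematological toxicity in CLL studies". That scale (Appendix 3) grades haemoglobin and platelets by "Decrease in platelets† or Hb‡ (nadir) from pretreatment value". Note c, marked on both rows, says that subjects with baseline cytopenia should have haemoglobin of at least 8 g/dL, platelets of at least 40 ×10³/mm³ and ANC of at least 1.0 ×10⁹/L "in order to proceed with the study treatment", with transfusion and growth factors permitted.

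**The concern.** A site managing one cytopenia has to read both cells of a row and the notes attached to it. In the Grade 3–4 row the two cells reach the same end, the subject off study treatment, at different times and from different recovery targets. In the Grade 1–2 row, a percentage-based grade and an absolute floor can point in different directions for the same count.

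The event is not rare. Section 1.2.4.9 reports Grade 3–4 cytopenia in 41% of ibrutinib subjects. Section 1.3.2.1 reports Grade 3–4 blood and lymphatic disorders in 15 of 51 subjects on obinutuzumab, and Grade 3–4 neutropenia in 5 of 6 subjects in the CLL11 run-in.

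At stake is which subjects are dosed, delayed or withdrawn. The reporting of treatment administration, study completion and protocol deviations promised in Section 10.1.1 also needs a single rule to measure against.

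**Working it through.** The plan gives no figure to reproduce here. The check sets the rules side by side and applies the grading scale.

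**1. The two limits in the Grade 3–4 row**

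| | Obinutuzumab cell | Ibrutinib cell | Section 6.3.1 |
|---|---|---|---|
| Clock | delay of a planned infusion | duration of toxicity or hold | duration of toxicity or hold |
| Limit | 8 weeks = 56 days | more than 28 days | more than 28 days |
| Recovery target | Grade ≤ 2 or baseline | Grade ≤ 1 or baseline | Grade ≤ 1 |
| At the limit | off study treatment | ibrutinib stopped **and** off study treatment | ibrutinib stopped |

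The clocks start at different times, so days cannot be compared directly. Section 5 puts the later infusions on study days 29, 57, 85, 113 and 141.

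- *Onset on the day an infusion is due (study day 57).* Toxicity reaches 28 days on day 57 + 28 = 85. The infusion delay is then 28 days, and the 8-week limit falls on day 57 + 56 = 113. Between days 85 and 113 an unresolved Grade 3–4 cytopenia is a permitted delay in one cell and a withdrawal in the other.
- *Onset on Cycle 2 Day 8 (study day 36).* The next infusion is due 57 − 36 = 21 days later. A 40-day cytopenia ends on day 76, so the infusion is 76 − 57 = 19 days late, well inside 56 days. Toxicity passed 28 days on day 64, when the infusion was only 64 − 57 = 7 days late.
- *After the Cycle 6 infusion (study day 141).* No obinutuzumab remains, so there is nothing to conflict.

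The conflict therefore exists while infusions remain, and its length depends on when the episode starts.

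**2. The recovery targets**

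Take a cytopenia that has improved to Grade 2 but has lasted more than 28 days. The obinutuzumab cell gives the full dose. The ibrutinib cell has not reached its target, and its 28-day limit has passed. The baseline alternative in note b does not remove this for haemoglobin or platelets on the Appendix 3 scale, because there the baseline value is by construction Grade 0. It does remove it for a subject whose baseline ANC already lay in the Grade 2 band (1000 to below 1500/µL).

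**3. Grade against floor in the Grade 1–2 row**

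Fall = (baseline − current) / baseline. Appendix 3: Grade 1 is 11–24%, Grade 2 is 25–49%.

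- Platelets 50 to 35: (50 − 35)/50 = 30%, Grade 2, below 40.
- Haemoglobin 9.5 to 7.5: (9.5 − 7.5)/9.5 = 21%, Grade 1, below 8.

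Baselines at which a breach is possible:

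| | Some Grade 2 values below floor | All Grade 2 values below floor |
|---|---|---|
| Platelets (×10³/mm³) | baseline < 40/0.51 = 78.4 | baseline < 40/0.75 = 53.3 |
| Haemoglobin (g/dL) | baseline < 8/0.51 = 15.7 | baseline < 8/0.75 = 10.7 |

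The Appendix 3 rule that makes any platelet count below 20 Grade 4 does not interfere: at the lowest eligible baseline, 40 × 0.51 = 20.4.

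ANC: Grade 2 begins at 1000/µL, which equals the 1.0 ×10⁹/L floor. No Grade 1–2 ANC value lies below it, so there is no conflict.

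**The case against.** Four counter-arguments carry weight.

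**Two drugs may have two hold limits.** True, and different limits or recovery targets would not by themselves be an error. The difficulty is the stated consequence. The ibrutinib cell first discontinues ibrutinib and then adds coming off study treatment as a further step, in the same terms as the obinutuzumab cell uses at 8 weeks. Reading it as ibrutinib alone would match Section 6.3.1, but would leave the second step with no content. The documents do not settle which is meant.

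**A footnote qualifies its row.** Note c can be read as an added condition for subjects with baseline cytopenia, and it says should rather than must. Its floors, and its allowance for transfusion and growth factors, match inclusion criterion 5, so it may be an entry condition. Against that, it is marked on both rows of an on-treatment table, covers only subjects with baseline cytopenia whereas criterion 5 covers everyone, and does not say when it applies. This is an ambiguity, not a proven contradiction.

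**Transfusion may resolve the haemoglobin case.** Appendix 3 grades haemoglobin before transfusion. If note c may be met afterwards, as criterion 5 allows, grade and floor can both be satisfied. Note c permits transfusion but does not say whether the floor may be met that way.

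**The size is easily overread.** A reader might infer that every cytopenia lasting 29 to 56 days is caught, or that nearly every anaemic subject breaches the floor. Neither follows. The clocks differ, nothing conflicts after the last infusion, and the baseline ranges show only where a breach is arithmetically possible. The 15.7 g/dL bound matters only as far up as a subject still counts as having baseline cytopenia. Neutropenia, the most frequent Grade 3–4 cytopenia in Section 1.2.4.9 (29%), does not enter the note c question at all.

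**Conclusion.** The point stands, with its two parts at different strengths.

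- **Contradiction.** While obinutuzumab infusions remain, a Grade 3–4 cytopenia that lasts more than 28 days, including one that has improved only to Grade 2, can fall within the permitted delay or qualify for a full dose under one cell and require withdrawal under the other. This rests on reading the same phrase alike in both cells. The text before the table and Section 6.3.1 do not resolve it.
- **Ambiguity.** For subjects with baseline cytopenia, a Grade 1–2 fall in platelets or haemoglobin can lie below note c's floor while the obinutuzumab cell excludes delay. It becomes a conflict only if note c applies at each dose. ANC is not affected, and the ibrutinib cell does not exclude delay.

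The documents do not say how often such episodes last beyond 28 days, so no frequency can be given.

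A reader might also infer that the conflict eats into the 3 non-responses that 29 of 32 leaves room for. The documents do not support that. Subjects taken off treatment stay in follow-up, Section 10.6 has all treated subjects assessed, Section 3.2.2 counts responses over the course of the study, and withdrawal is nowhere defined as non-response. Section 10.4 does bar replacement of subjects who withdraw from the study for toxicity, so an effect is possible, but its size cannot be computed.

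**What to change.** Reconcile Table 7, the text before it, note c and Section 6.3.1. The revised wording should state:

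1. whether coming off study treatment in the ibrutinib cell also ends obinutuzumab and, if it does, which cases of cytopenia the 8-week obinutuzumab allowance still covers;
2. what happens to each drug when a cytopenia has improved to Grade 2 but has lasted more than 28 days;
3. whether note c applies at entry only or at each dose, and whether its floors may be met after transfusion;
4. which rule prevails when the grade and the floor disagree.

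Which rule stands is for the clinical team; this review takes no position on it. The cost is a wording amendment, with the supplier and IRB review that Section 13 requires. Sample size, design boundaries and planned analyses are unchanged. The reconciled rule would then be the reference for the deviations and completion status described under Section 10.1.1.

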6.4 CONCOMITANT, EXCLUDED THERAPIES AND DRUG-DRUG INTERACTIONS

6.4.1 Permitted Concomitant Medications

Concomitant therapy includes any prescription medications or over-the-counter preparations used by a subject between the 14 days preceding the study entry evaluation and the early study treatment termination visit/study treatment completion visit. All concomitant medications should be reported to the investigator and recorded on the appropriate electronic Case Report Form (eCRF).

Supportive medications in accordance with standard practice (such as for emesis, diarrhea, etc.) are permitted. Use of neutrophil growth factors (filgrastim and pegfilgrastim) or red blood cell growth factors (erythropoietin) is permitted per institutional policy and in accordance with the ASCO guidelines (Smith et al., 2006). Transfusions may be given in accordance with institutional policy.

Short courses (≤14 days) of steroid treatment for non-cancer related medical reasons (eg, joint inflammation, asthma exacerbation, rash, antiemetic use and infusion reactions) at doses that do not exceed 100mg per day of prednisone or equivalent are permitted.

The following may be considered: localized hormonal or bone sparing treatment for non-B-cell malignancies, and localized radiotherapy for medical conditions other than the underlying B-cell malignancies.

Treatment for autoimmune cytopenias are permitted for <14 days at doses that do not exceed 100 mg per day of prednisone or equivalent.

Ibrutinib + GA101 - Obinutuzumab. University of California, San Diego

6.4.2 Medications to be used with Caution

6.4.2.1 CYP3A- Inhibitors/Inducers

Ibrutinib is metabolized primarily by CYP3A4. Concomitant use of ibrutinib and drugs that strongly or moderately inhibit CYP3A can increase ibrutinib exposure and therefore strong CYP3A inhibitors should be avoided.

- If a strong CYP3A inhibitor (eg, ketoconazole, indinavir, nelfinavir, ritonavir, saquinavir, clarithromycin, telithromycin, itraconazole, nefazodone, cobicistat, and posaconazole) must be used, reduce ibrutinib to 140 mg for the duration of the inhibitor use or withhold ibrutinib treatment temporarily (for 7 days or less). Subjects should be monitored for signs of ibrutinib toxicity.
- If a moderate CYP3A inhibitor (eg, fluconazole, voriconazole, erythromycin, amprenavir, aprepitant, atazanavir, ciprofloxacin, crizotinib, diltiazem, fosamprenavir, imatinib, verapamil, amiodarone, and dronedarone) is indicated, reduce ibrutinib dose to 140 mg for the duration of the inhibitor use.
- No dose adjustment is required in combination with mild inhibitors.
- Avoid grapefruit and Seville oranges during ibrutinib treatment as these contain moderate inhibitors of CYP3A (see Section 6.1.2).

Avoid concomitant use of systemic strong CYP3A inducers (eg, carbamazepine, rifampin, phenytoin, and St. John's Wort). Consider alternative agents with less CYP3A induction.

A list of common CYP3A inhibitors and inducers is provided in appendix 5. For further information, please refer to the current version of the IB and examples of inhibitors, inducers, and substrates can be found at http://medicine.iupui.edu/clinpharm/ddis/maintable/. This website is continually revised and should be checked frequently for updates.

6.4.2.2 Drugs That May Have Their Plasma Concentrations Altered by Ibrutinib

In vitro studies indicated that ibrutinib is not a substrate of P-glycoprotein (P-gp), but is a mild inhibitor (with an IC $_{50}$ of 2.15 µg/mL). Ibrutinib is not expected to have systemic drug-drug interactions with P-gp substrates. However, it cannot be excluded that ibrutinib could inhibit intestinal P-gp after a therapeutic dose. There is no clinical data available; therefore, co-administration of narrow therapeutic index P-gp substrates (eg, digoxin) with ibrutinib may increase their blood concentration and should be used with caution and monitored closely for toxicity.

6.4.2.3 QT Prolonging Agents

Any medications known to cause QT prolongation should be used with caution; periodic ECG and electrolyte monitoring should be considered.

Ibrutinib + GA101 - Obinutuzumab. University of California, San Diego

6.4.2.4 Antiplatelet Agents and Anticoagulants

Warfarin or vitamin K antagonists should not be administered concomitantly with Ibrutinib. Supplements such as fish oil and vitamin E preparations should be avoided. Use Ibrutinib with caution in subjects requiring other anticoagulants or medications that inhibit platelet function. Subjects with congenital bleeding diathesis have not been studied. Ibrutinib should be held at least 3 to 7 days pre- and post-surgery depending upon the type of surgery and the risk of bleeding (see Section 6.5).

Subjects requiring the initiation of therapeutic anticoagulation therapy (other than warfarin or a vitamin K antagonist) during the course of the study should have treatment with ibrutinib/ placebo held, the sponsor's medical monitor should be contacted, and ibrutinib/placebo should not be restarted until the subject is clinically stable and the reinitiation of ibrutinib/placebo is approved by the sponsor's medical monitor. Subjects should be observed closely for signs and symptoms of bleeding. No dose reduction is required when study drug is restarted.

6.4.3 Prohibited Concomitant Medications

Any chemotherapy, anticancer immunotherapy, experimental therapy, radiotherapy or live viral vaccines are prohibited while the subject is receiving ibrutinib treatment.

Corticosteroids for the treatment of an underlying disease are prohibited. Corticosteroids for the treatment of non-cancer related reasons for longer than 14 days and/or at doses >100mg of prednisone or its equivalent are prohibited.

Erythropoietic growth factors (eg, erythropoietin) and neutrophil growth factors (eg, filgrastim and peg-filgrastim) are also prohibited during (eg, initial treatment, DLT assessment period).

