4.1 INCLUSION CRITERIA

Subjects must meet the following criteria for study entry:

- 1. Diagnosis of CLL:
- Monoclonal B-cells co-expressing ≥ one B-cell marker (CD19, CD20, or CD23) and CD5 in peripheral blood or lymph node.
 - 2. Indication for treatment as defined by the IWCLL Guidelines:
- Massive (i.e. > 6 cm below the left costal margin) or progressive/ symptomatic splenomegaly OR
- Massive lymph nodes or nodal clusters (i.e. > 10 cm in longest diameter), or progressive / symptomatic lymphadenopathy OR
 - Presence of disease-related constitutional symptoms:
 - Weight loss ≥ 10% over the preceding 6 months
- Significant fatigue (i.e., ECOG PS 2 or worse; inability to work or perform usual activities).
- Fevers higher than 100.5°F or 38.0°C for 2 or more weeks without other evidence of infection.
 - Night sweats for more than 1 month without evidence of infection.

Ibrutinib + GA101 – Obinutuzumab. University of California, San Diego

- Progressive lymphocytes with an increase of \geqslant 50% over a 2-month period or an anticipated doubling time of less than 6 months. OR
- Evidence of progressive marrow failure as manifested by the development of, or worsening of, anemia and / or thrombocytopenia.
- Autoimmune anemia and / or thrombocytopenia poorly responsive to corticosteroids or other standard therapy.
 - 3. No previous treatment for CLL.
 - 4. Males and females 65 years of age and older. Subjects < 65 years of age that meet any of the following criteria:
 - Subjects that refuse to be treated with chemotherapy based agents (This should be documented in the consent form).
 - Subjects that are not candidates for treatment with chemotherapy agents based on any of the following:
 - ECOG Performance status ≥ 2
 - Cumulative Illness Rating Scale (CIRS score) ≥ 6 (Appendix 6)
 - Creatinine clearance <70 mL/min using the Cockcroft-Gault Equation.
 - 5. Laboratory parameters as specified below:
 - Hematologic: Hemoglobin \geq 8 g/dL (may be post-transfusion); platelet count \geq 40 x10³/mm³ (may be post-transfusion). Absolute neutrophil count \geq 1.0 × 10⁹ cells/L (Growth factor use is allowed).
 - Hepatic: Total Bilirubin < 3 x ULN, and ALT and AST < 3 x ULN
 - Renal: Creatinine clearance > 30 mL/min (Calculated according to institutional standards or using Cockcroft–Gault formula. Subjects with requirement of hemodialysis will be excluded).
 - 6. Anticipated survival of at least 6 months.

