6.2.9 Administration of Granulocyte Colony-Stimulating Factor

G-CSF may be administered as primary prophylaxis in each cycle of therapy, as per the American Society of Clinical Oncology (ASCO) guidelines or each site's institutional standards.

Ibrutinib + GA101 – Obinutuzumab. University of California, San Diego

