6.3 DOSE MODIFICATIONS AND DELAYS FOR IBRUTINIB AND GA101 – OBINUTUZUMAB

6.3.1 Dose Hold, Reduction, or Discontinuation of Ibrutinib

Treatment with Ibrutinib should be held for any unmanageable, potentially study drug-related toxicity that is Grade 3 or higher in severity. Subjects who require anticoagulant treatment (eg, heparin and/or warfarin) should have study drug hold until stable on anticoagulant therapy.

Ibrutinib may be held for a maximum of 28 consecutive days of toxicity. Ibrutinib should be discontinued in the event of a toxicity > Grade 1 lasting > 28 days.

A hematologic AE grading scheme for hematologic toxicity is included in Appendix 3.

The actions in Table 4 should be taken for the following toxicities:

- Grade 4 ANC (< 500/μL) for > 7 days (Neutrophil growth factors are permitted per ASCO guidelines) (Smith et al., 2006) and use must be recorded in CRF.
- Grade 3 or 4 platelets (< 50,000/µL); or, in subjects with baseline thrombocytopenia, a platelet decrease of 50-74% from baseline in presence of bleeding.

Ibrutinib + GA101 - Obinutuzumab. University of California, San Diego

- Grade 4 Platelets (< 25,000/μL); or, in subjects with baseline thrombocytopenia, decrease of > 75% from baseline or < 20,000/μL, whichever is higher.
 - Grade 3 or 4 nausea, vomiting, or diarrhea, if persistent despite optimal antiemetic and/or anti-diarrheal therapy, or any other Grade 4 toxicity and any unmanageable Grade 3 toxicity.

Table 4 Dose modifications or discontinuation actions for Ibrutinib

Occurrence ≥ G3	Action	
AE		
1 st	Hold Ibrutinib until recovery to Grade ≤ 1 or baseline; may restart	
	at original dose level	
2 nd	Hold Ibrutinib until recovery to Grade ≤ 1 or baseline; restart at	
	one dose level lower (280 mg daily)	
3 rd	Hold Ibrutinib until recovery to Grade ≤ 1 or baseline; restart at	
	one dose level lower (140 mg daily)	
4 th	Discontinue Ibrutinib	

6.3.2 Dose Modifications for Ibrutinib for Hepatic Impaired Subject

Ibrutinib is metabolized in the liver and therefore subjects with clinically significant hepatic impairment at the time of screening (Child- Pugh class B or C) are excluded from study participation.

Subjects while on study who develop significant clinical and/or laboratory signs and/or symptoms of liver dysfunction (e.g., transaminitis, jaundice, etc.) in the opinion of the investigator, should be assessed with the Child-Pugh Score (Table 5) to determine a dose reduction of Ibrutinib as described in Table 6:

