10.2.2 Safety Analysis

All subjects who have at least one dose of Ibrutinib and/or one infusion of GA101 – Obinutuzumab, and a safety follow-up, whether withdrawn prematurely or not, will be included in the safety analysis.

10.2.3 Clinical Adverse Events

All adverse events, including unrelated adverse events, will be listed and graded according to the NCI-CTCAE grading system (Version 4.0) (Appendix 7). The proportion of subjects with treatment-related adverse events, overall, and by body system, will be tabulated. In addition, subjects with treatment-related adverse events, SAEs, and adverse events leading to withdrawal will be listed overall and, if appropriate, distributions by body system will be provided.

10.2.4 Definition of Dose Limiting Toxicity (DLT)

Dose limiting toxicity (DLT) is defined as any of the adverse events (AEs) noted below that are considered by the investigator to be possibly related or related to Ibrutinib / GA101 - Obinutuzumab treatment. For the purpose of defining DLTs, AE will be tabulated and assessed based on the signs and symptoms present during the first cycle of treatment (Day 1 - 28). Toxicity will be graded according to the NCI-Common Terminology Criteria for Adverse Events (CTCAE) version 4.0 (Appendix 7) except for hematological toxicities that will be graded according to the IWCLL guidelines (Hallek et

Ibrutinib + GA101 - Obinutuzumab. University of California, San Diego

al., 2008) (Appendix 3) For subjects with a normal neutrophil count, platelet count, and/or hemoglobin value at baseline, the NCI-CTCAE v4.0 grading system will be used. Dose limiting toxicity will include possibly related or related events that are Grade ≥ 3 that do not resolve to Grade ≤ 1within 14 days of initiation despite appropriate medical management. The following exceptions will apply:

Non Hematologic:

- ≥ Grade 3 nausea, vomiting, or diarrhea only if uncontrolled by maximal antiemetic/antidiarrheal therapy.

Hematologic:

Hematologic toxicity will be graded according to the IWCLL guidelines (Hallek et al., 2008) - (Appendix 3), with dose-limiting hematologic toxicity defined as follows:

- ≥ Grade 4 granulocytopenia lasting ≥ 14 days. Note that per IWCLL guidelines, subjects are evaluable for toxicity related to granulocytopenia only if the pre-treatment ANC is >1.0 x10⁹/L.

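### Growth factors are both permitted and prohibited in Cycle 1, so the granulocytopenia DLT count in the run-in depends on an unresolved rule

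*Combined protocol and SAP*

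**What the plan says.** **Permissive text.** Section 6.2.9 states that "G-CSF may be administered as primary prophylaxis in each cycle of therapy", under ASCO guidelines or institutional standards. Section 6.4.1 states: "Use of neutrophil growth factors (filgrastim and pegfilgrastim) or red blood cell growth factors (erythropoietin) is permitted per institutional policy". Section 6.3.1, on ibrutinib holds for prolonged Grade 4 neutropenia, notes: "Neutrophil growth factors are permitted per ASCO guidelines". Table 7 note c, on subjects with baseline cytopenia, adds: "Transfusion and Growth factors will be permitted and must be documented in the medical chart". At entry, the neutrophil criterion in Section 4.1 carries the remark "Growth factor use is allowed". None of these makes an exception for Cycle 1.

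**Prohibitive text.** Section 6.4.3 says that erythropoietic and neutrophil growth factors "are also prohibited during (eg, initial treatment, DLT assessment period". Only bracketed examples follow the word during; the period itself is never named.

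**DLT definition.** Section 10.2.4 assesses DLTs on events "present during the first cycle of treatment (Day 1 - 28". The granulocytopenia criterion is "Grade 4 granulocytopenia lasting ≥ 14 days" (Grade 4 or worse). Appendix 3 makes G-CSF use irrelevant to the grade but asks that it be documented. Section 1.3.4.3 reports that myeloid growth factors bring neutrophils back to normal rapidly.

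**Decision rule.** Under Section 10.2.6, two or more DLTs in the first six subjects put enrollment on hold. Table 8 gives the probability of halting for true DLT rates from 5% to 50%.

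**The concern.** Every cycle includes Cycle 1, and Cycle 1 is the DLT window, so Sections 6.2.9 and 6.4.3 cannot both be followed. Two people treating or auditing the same run-in subject could reach opposite conclusions and each cite the protocol. A subject could also enter on growth-factor support, as Section 4.1 allows, and then fall under the 6.4.3 prohibition.

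The choice reaches the Phase IB primary endpoint because the granulocytopenia criterion is measured in days. A drug that speeds neutrophil recovery can turn a qualifying event into a non-qualifying one. With six subjects and a threshold of two, reclassifying one event can reverse the hold decision. The protocol does not say how a growth-factor-supported neutrophil count enters the DLT definition.

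Sections 6.4.1 and 6.4.3 conflict on erythropoietin as well. That part is a matter of wording for the run-in, since neither hematologic criterion listed in Section 10.2.4 is based on hemoglobin.

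**Working it through.** **Step 1. The passages side by side**

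| Place | Rule on growth factors | Covers Cycle 1? |
|---|---|---|
| 6.2.9 | G-CSF permitted as primary prophylaxis | Yes, every cycle |
| 6.3.1 | Neutrophil growth factors permitted | No exception stated |
| 6.4.1 | Neutrophil growth factors and erythropoietin permitted | No exception stated |
| Table 7 note c | Permitted, for subjects with baseline cytopenia | No exception stated |
| 6.4.3 | Both classes prohibited | Yes, the DLT period is named as an example |

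The conflict between 6.2.9 and 6.4.3 is direct. The other three are general permissions to which 6.4.3 could be an exception, but nothing in the text says so.

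**Step 2. Reproduce Table 8**

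Inputs: n = 6, hold at two or more DLTs (Section 10.2.6).

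P(halt) = 1 − (1−p)^6 − 6p(1−p)^5.

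At p = 0.30: 1 − 0.1176 − 0.3025 = 0.580. Table 8 prints 58%.

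Expected toxicities = 3p + 3p × P(0 or 1 DLT in the first 3). At p = 0.30: 0.9 + 0.9 × 0.784 = 1.606. Table 8 prints 1.61.

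All ten rows reproduce in both columns, so the table is arithmetically right.

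**Step 3. How a lower counted rate would act**

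Let p be the DLT rate without growth factors, s the share of DLTs that are granulocytopenia, and m the fraction of those that growth factors shorten below 14 days. The counted rate is p × (1 − s × m). The documents give neither s nor m, so both are assumed below, with p = 0.30.

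| Share s | Averted m | Counted rate | P(halt) |
|---|---|---|---|
| any | 0 | 0.3000 | 58.0% |
| 0.25 | 0.5 | 0.2625 | 49.5% |
| 0.25 | 1 | 0.2250 | 40.6% |
| 0.50 | 0.5 | 0.2250 | 40.6% |
| 0.50 | 1 | 0.1500 | 22.4% |
| 0.75 | 0.5 | 0.1875 | 31.4% |
| 0.75 | 1 | 0.0750 | 6.9% |

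If 6.4.3 is followed, m = 0 and the first row applies.

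**The case against.** Several points on the other side stand.

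- **The criterion stays in force.** Grade 4 granulocytopenia of 14 days or more is a DLT whichever section is followed. Growth factors may make it rarer but do not remove it. The trial is single-center, so differing practice between sites is not the issue.
- **The rest of the DLT definition is untouched.** The thrombocytopenia, infusion-reaction and gastrointestinal criteria do not rest on the neutrophil count. The general rule already counts events that persist despite appropriate medical management, so counting toxicity under supportive care is not foreign to it.
- **Neutropenia would still be seen.** Serious neutropenia is an event of special interest with expedited reporting (Section 11.4.3.7), and the DSMB reviews safety before Phase II (Section 11.4.5).
- **Growth-factor use is already recorded** under Sections 6.3.1 and 6.4.1, Table 7 note c and Appendix 3.

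A reader might infer that the run-in cannot be interpreted, or that Table 8 is wrong. The documents support neither. The ambiguity concerns one criterion. Table 8 makes no assumption about growth factors; their use changes which row applies.

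A reader might also infer that neutropenia is the main DLT risk, because Section 1.3.2.1 reports Grade 3–4 neutropenia in 5 of 6 subjects of the obinutuzumab–chlorambucil run-in. That regimen differs, the duration is not given, and no stopping criterion was met there. In the monotherapy study in the same section, 9 of 13 CLL subjects had Grade 3–4 neutropenia with no DLTs, and the three of those nine who did not receive G-CSF recovered spontaneously. These data show that neutropenia is common, not how often it would qualify as a DLT.

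None of this settles which rule applies in Cycle 1.

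**Conclusion.** The contradiction holds and needs no assumption: the plan both permits and prohibits neutrophil growth factors in the DLT window and gives no order of precedence. The consequence is limited. If the permissive sections are followed, the granulocytopenia DLT can be under-counted relative to a run-in without growth factors, and the 2-of-6 rule would then be less likely to hold enrollment. If 6.4.3 is followed, this does not arise.

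The size is unknown. The range of 49.5% to 6.9%, against 58.0%, rests on an assumed 30% DLT rate, assumed neutropenia shares of one quarter to three quarters, and an assumed half to all of those events averted. It shows how sensitive a six-subject rule is and does not estimate what happened or will happen. The drop to 22.4% is one such scenario (half of DLTs, all averted) and should not be read as a finding. The point should be addressed because it bears on the Phase IB primary endpoint and is cheap to resolve.

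**What to change.** 1. Complete the sentence in Section 6.4.3 so that it names the period it covers, and reconcile it with Sections 6.2.9, 6.3.1 and 6.4.1 and Table 7 note c. Which rule should apply is for the sponsor and investigator; this review takes no position.
2. State in Section 10.2.4 how a neutrophil count obtained under growth-factor support counts toward the 14-day criterion.
3. In the run-in report to the DSMB, list Cycle 1 growth-factor use for each of the six subjects, and give the DLT count with those subjects flagged.

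The cost is protocol wording and one column in a short report. The data for the flag are already required to be documented, so it can be produced even if the run-in is complete. Table 8 needs no change.
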